8.8. Procedure at Disease Progression/recurrence

If a patient has a local or distant relapse, new primary cancer (including contralateral breast, lung, and oesophagus) the following procedures should be followed:

- Routine clinical, histological and imaging information should be collected on the disease relapse and entered into the relevant FAST-Forward Boost eCRF.
- The patient should be treated according to local protocol for relapse/new primary cancer.

8.9. Discontinuation from Treatment

Participants may discontinue from trial treatment at any time at their own request, or they may be discontinued at the discretion of the Principal Investigator. Reasons for discontinuation may include:

- Disease progression or recurrence
- Unacceptable toxicity
- Pregnancy.

Participants who discontinue treatment should continue to be followed up.

8.10. Change in Participation Status

Participants may choose to change, reduce, or stop their participation after joining the trial. Within FAST-Forward Boost the following changes in participation are possible:

- Stopping trial specific follow up – data will continue to be requested from routine visits.
- Stopping routine clinical follow up – data will continue to be requested from details in the patients' medical record (e.g. date of progression/death).
- Stopping participation in patient reported outcome questionnaires
- Stopping participation in optional sub studies.
- Stopping donated samples being used in FAST-Forward Boost research/analysis
- Stopping future sharing of data/samples.
- Withdrawal of consent for any further data to be submitted – data up to the point of withdrawal will be retained as described in the patient information sheet.

Changes in participation should be led by the participant, and no assumptions should be made on their behalf. If this occurs, a change in participation status form should be submitted to ICR-CTSU to report the details of the reduction in participation. For further guidance on the types of change in participation status and guidance on loss of contact, please refer to trial guidance notes.

8.11. Schedule of Assessments

FAST-Forward Boost Assessments Additional Early Side-Effects Sub-Study assessments	Pre-treatment assessments	On-treatment Assessments			End of treatment assessments				Post-treatment assessments					
		Week 1	Week 2	Week 3	Week 4	Week 5	Week 6	Week 7	3 months	1 year (in clinic)	2 years	3 years (in clinic)	4 years	5 years (in clinic)
Clinician reported														
Medical history	x													
Weight and height measurement	x													
Breast assessment (trial-specific and Harvard-Harris scale)	x									x	x		x	
Lung toxicity assessment (RTOG)	x								x	x				
Collection of baseline blood sample (optional)	x													
Additional blood samples – control group (optional)					x	x								
Additional blood samples – test groups (optional)		x	x											
Skin, breast and oesophageal toxicity assessment (CTCAE V5.0)	x	x	x	x	x	x								
Late toxicity and adverse events										x	x	x	x	
Recurrence and survival										x	x	x	x	
Patient reported demographics														
Demographics booklet (UK only)	x													
Patient reported outcomes (non-mandatory for main trial)														
Health related quality of life (EORTC QLQ-C30 and QLQ-BR23)	x					x			x	x	x	x	x	x
Body Image Scale (BIS)	x					x			x	x	x	x	x	x
Hospital Anxiety and Depression Scale (HADS)	x													
Fatigue (EORTC QLQ-FA-12)	x	x	x	x	x		x	x	x	x	x	x	x	x
Overall quality of life (EQ5D-5L)	x	x	x	x					x	x	x	x	x	x
Patient assessed oesophageal toxicity (PRO-CTCAE v5.0) for patients receiving radiotherapy to IMC only	x				x									
Out of pocket expenditure (UK only)		x	x	x										
Health care resource use (UK only)									x	x	x	x	x	
Early Skin, breast, and oesophageal toxicity assessment (PRO-CTCAE V5.0 and trial specific)	x	x	x	x	x	x	x	x						
Longer term Radiotherapy Symptoms (breast & arm/shoulder trial specific)	x								x	x	x	x	x	x
Disease status										x	x	x	x	x

8.12. Treatment Timelines

Radiotherapy should commence as soon as possible and ideally within 4 weeks of randomisation. It is advised that radiotherapy starts within 8 weeks of surgery and/or last dose of chemotherapy when possible. Timelines from systemic therapy to start of radiotherapy should otherwise be observed as per standard of care.

(please see section 8.15 for advice about timing with systemic therapy).

8.13. Radiotherapy Planning & Treatment

Radiotherapy imaging, positioning, outlining, planning and treatment should be carried out in accordance with the guidelines in the current version of the radiotherapy planning document, available on request from ICR-CTSU ([contact]).

Radiotherapy prescription doses are as follows:

Control Group: 40Gy/15#/ 3 weeks to breast +/- nodes with 48Gy/15#/ 3 weeks to the boost volume.

Test Group 1: 26Gy/ 5#/ 1 week to breast +/- nodes with 31Gy/5#/ 1 week to the boost volume.

Test Group 2: 26Gy/ 5#/ 1 week to breast +/- nodes with 30Gy/5#/ 1 week to the boost volume.

Where a nodal boost is prescribed this should be 48Gy/15# in the control group and 30Gy/5# in either of the test groups.

8.14. Treatment Scheduling and Gaps

Treatment can start on any day of the week. Patients should not have a break in treatment where possible. Where interruptions are due to breakdown or unavailability of the treatment machine, patients should be transferred to a matched treatment machine in the first instance.

Where this is not possible, the gap should be kept to a minimum in the event of machine service or breakdown. If the treatment machine is unavailable for more than 7 consecutive days (including the weekend days), please contact the RTTQA team and the FAST-Forward Boost Trial team.

8.15. Concomitant Therapy

TDM-1 can be given concomitantly with radiotherapy but, in the test groups, it is recommended that TDM-1 should not be given within 4 days prior to (or after) a fraction of radiotherapy. For the control group, it is accepted that one TDM-1 dose will be given on the same day as a radiotherapy fraction.

Where CDK4/6 inhibitors are recommended, these should ideally be given no earlier than 7 days following completion of radiotherapy. If CDK4/6 inhibitors have been started prior to trial randomisation, they should be stopped at least 7 days prior to the first radiotherapy fraction and can be restarted 7 days after the final fraction.

Immunotherapy can be started before radiotherapy, but doses of immunotherapy should not be given within 7 days prior to the first fraction of radiotherapy or within 7 days of the last fraction of radiotherapy.

Concomitant endocrine therapy, bisphosphonate, denosumab, trastuzumab and pertuzumab *are* permitted.

Other chemotherapy agents (including adjuvant anthracyclines, taxanes and capecitabine) and other biological/targeted therapies (e.g. PARP inhibitors) are not permitted to be delivered concomitantly with radiotherapy. Standard departmental protocols of timing of these agents in relation to radiotherapy should be followed. Contact the ICR-CTSU if any clarification around systemic therapies is required.

It is recommended that radio-sensitising agents such as methotrexate are discontinued for at least one week prior to and after completion of radiotherapy. Otherwise, all medication considered necessary for the patient's welfare, and which is not expected to interfere with the evaluation of the treatment may be given at the discretion of the investigator. All concomitant medications (including start/stop dates, dose frequency, route of administration and indication) must be recorded in the patient's notes.

8.16. Radiotherapy Quality Assurance (QA)

The radiotherapy quality assurance (RT QA) programme for the FAST-Forward Boost Trial has been designed and will be implemented by the UK National Radiotherapy Trials QA (RTTQA) Group. The components of the FAST-Forward Boost QA programme are described in the FAST-Forward Boost Radiotherapy Planning and Delivery guidelines ("Quality Assurance (QA) pack"). There are pre-trial QA components and on trial QA components; please refer to guidelines.

The details of the programme are available on the RTTQA group website <https://rttrialsqa.org.uk/>. Please contact the RTTQA team for the benchmark cases and radiotherapy guidelines.

9. SAFETY REPORTING

9.1. Definitions

Adverse Event (AE)

An AE is any untoward medical occurrence in a patient administered a study treatment; the event does not necessarily have a causal relationship with the treatment.

Serious Adverse Event (SAE)

An SAE is any untoward medical occurrence that occurs after the first radiotherapy treatment and within 30 days of the last treatment of radiotherapy and

- results in death,
- is life-threatening,
- requires hospitalisation or prolongation of existing inpatients' hospitalisation,
- results in persistent or significant disability or incapacity,
- is a congenital anomaly or birth defect.

Important adverse events that are not immediately life-threatening or do not result in death or hospitalisation but may jeopardise the subject or may require intervention to prevent one of the other outcomes listed in the definition above, may also be considered serious.

Progression of the indicated disease and death due to progression of the indicated disease are not considered SAEs and do not need to be reported as such but should be reported on the appropriate eCRF as required.

Pregnancy or aid in the conception of a child whilst participating in a trial is not itself considered an SAE but should be followed up for congenital anomalies or birth defects.

Serious Adverse Reaction (SAR)

A serious adverse reaction is an SAE that is suspected as having a causal relationship to the trial treatment, as assessed by the investigator responsible for the care of the patient. A suspected causal relationship is defined as possibly, probably, or definitely related (see definitions of causality table).

Related Unexpected Serious Adverse Event

An adverse event that meets the definition of serious and is assessed by the CI or nominative representative as:

“Related” – that is, it resulted from administration of any of the research procedures, and

“Unexpected” – that is, the type of event is not listed in the protocol as an expected occurrence (see section 9.4))

Definitions of causality

Relationship	Description
Unrelated	There is no evidence of any causal relationship with the trial treatment
Unlikely	There is little evidence to suggest there is a causal relationship (e.g. the event did not occur within a reasonable time after administration of the trial treatment). There is another reasonable explanation for the event (e.g. the patient's clinical condition, other concomitant treatment)
Possible	There is some evidence to suggest a causal relationship (e.g. because the event occurs within a reasonable time after administration of the trial treatment). However, the influence of other factors may have contributed to the event (e.g. the patient's clinical condition, other concomitant treatments)
Probable	There is evidence to suggest a causal relationship, and the influence of other factors is unlikely
Definitely	There is clear evidence to suggest a causal relationship, and other possible contributing factors can be ruled out
Not assessable	There is insufficient or incomplete evidence to make a clinical judgement of the causal relationship.

9.2. Reporting Adverse Events to ICR-CTSU

For the patients in the early side-effects sub-study:

Any toxicity, sign or symptom that occurs after commencement of radiotherapy treatment and up to 7 weeks since the start of radiotherapy, which is not unequivocally due to progression of disease, should be considered an Adverse Event (AE) and reported on the relevant eCRF/(e)PRO booklet and submitted to ICR-CTSU.

All patient's radiotherapy related toxicities will be collected on the eCRF/(e)PRO as per the schedule of assessment.

The severity of AEs should be graded according to the NCIC-CTC criteria v5. For each AE, the highest grade observed since the last visit should be reported.

Whenever one or more toxicity/sign/symptom corresponds to a disease or a well-defined syndrome only the main disease/syndrome should be reported.

9.3. Reporting of Serious Adverse Events to ICR-CTSU

Any SAE that occurs after commencement of radiotherapy treatment and up to 30 days following the last fraction of radiotherapy treatment must be reported. All SAEs should be reported to ICR-CTSU within 24 hours of the Principal Investigator (or designated representative) becoming aware of the event, by completing the FAST-Forward Boost SAE form in the trial database.

As much information as possible, including the Principal Investigator's assessment of causality, must be reported to ICR-CTSU in the first instance. Additional follow up information should be reported as soon as it is available. All SAE forms must be electronically reviewed and approved by the Principal Investigator or designated representative.

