1. INTRODUCTION

1.1. Background/rationale for the trial

Radiotherapy is an important component of breast cancer treatment for many people: Breast cancer is the commonest cancer in the UK and radiotherapy is integral to the curative pathway for 37,000 UK people/year(1). Improvements in treatment, including radiotherapy and systemic therapies, have lowered disease recurrence rates but it remains the case that radiotherapy reduces the risk of local recurrence by up to two-thirds translating into improved breast cancer survival for the majority. Younger patients, and those whose disease expresses more aggressive biology, such as triple negative breast cancer, may have the most to gain from radiotherapy(2, 3) and are the population considered in this trial.

Radiotherapy impacts on the lives of people with breast cancer during treatment and for many years after cancer is cured: Radiotherapy can lead to early and long-term side-effects in breast and adjacent organs with impact on quality of life and wellbeing(2, 4). Acute side-effects include skin changes and fatigue which affect nearly all patients, peaking in the 2-4 weeks after radiotherapy. These tend to be mild for most patients. Symptomatic lung inflammation (pneumonitis) is rare (peaking around 3 months after radiotherapy in up to 2% of patients needing radiotherapy to lymph nodes behind the breastbone) but causes cough, breathlessness and fatigue when it occurs(5). Late breast radiotherapy side-effects include changes in breast appearance, notably breast shrinkage, which increase in incidence over time affecting around 16% people by 5 years(6). Lymphoedema affects 1 in 10 patients but can be lifelong when it occurs(5, 7). Major radiotherapy side-effects, including heart disease and second cancer, are rare (for example the risk of second lung cancer in non-smokers treated with modern radiotherapy techniques including breath-hold is <1 in 1000 at 20-years post-radiotherapy)(8).

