8.5. Timing of on-treatment assessments

Participants in the Control Group will receive radiotherapy over three weeks. Participants in Test Groups 1 and 2 will receive radiotherapy over one week. Assessments should be completed by all participants at the end of each week from the start of radiotherapy:

- Participants in the Control Group will complete these assessments whilst receiving treatment at the end of weeks 1, 2 and 3 (i.e. at fraction 5, at fraction 10 and at final treatment).
- For participants in the Test Groups, the week 1 assessment will be completed at the end of their treatment week (i.e. at fraction 5), and then week 2 and week 3 assessments will take place 7 days and 14 days after their final treatment, respectively.

In the unlikely event of treatment interruptions, the timing of these weekly assessments should remain scheduled in accordance with the originally planned start and end dates.

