Timing of assessments (assuming no treatment interruptions*):

	Control Group	Test Group
Week 1	At fraction 5	At fraction 5
Week 2	At fraction 10	7 days after final fraction
Week 3	At fraction 15	14 days after final fraction
Week 4	7 days after final fraction	21 days after final fraction
Week 5	14 days after final fraction	28 days after final fraction
Week 6	21 days after final fraction	35 days after final fraction
Week 7	28 days after final fraction	42 days after final fraction

*In the unlikely event of treatment interruptions, the timing of these weekly assessments should remain scheduled in accordance with the originally planned start and end dates.

Month 3

The following assessments should be conducted at 3 months after the start of radiotherapy for all participants:

- Lung toxicity assessment (RTOG) (*can be conducted by remote consultation*)
- Participants who have consented to complete PRO questionnaires will be sent/given a Follow-up (e)PRO booklet, including the following questionnaires (*for UK participants this will be coordinated by ICR-CTSU*):
 - EORTC QLQ-C30 and QLQ-BR23
 - Body Image Scale (BIS)
 - Fatigue (EORTC QLQ FA12)
 - EQ-5D-5L

- Radiotherapy symptoms (breast & arm/shoulder trial specific, used in previous trials).
- Patient reported health care resource use (UK only)

Additional assessments at month 3 for EARLY SIDE-EFFECTS SUB-STUDY ONLY

Patients will be sent the sub study specific “Follow Up Assessments – 3 months” (e)PRO booklet, containing the following additional questionnaires (*this will be coordinated by ICR-CTSU*):

- Patient assessed skin, breast, and oesophageal toxicity assessment (PRO-CTCAE V5.0 and trial specific questions as used in previous trials).

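### The SAE window ends 30 days after the last fraction, so from treatment start it is 14 days shorter in the 1-week groups, and raw by-arm SAE counts would tend to favour them

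*Protocol*

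**What the plan says.** Section 9.3 of the protocol sets the reporting duty: "Any SAE that occurs after commencement of radiotherapy treatment and up to 30 days following the last fraction of radiotherapy treatment must be reported". Section 9.1 builds the same limit into the definition, since an SAE is an event that "occurs after the first radiotherapy treatment and within 30 days of the last treatment of radiotherapy" and meets a seriousness criterion. An event after that limit is not an SAE at all.

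Section 8.5 gives the treatment durations: "Participants in the Control Group will receive radiotherapy over three weeks", and "Participants in Test Groups 1 and 2 will receive radiotherapy over one week".

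The acute toxicity data run on a different clock. Section 9.2 collects adverse events in the early side-effects sub-study "up to 7 weeks since the start of radiotherapy", the weekly assessments in sections 8.5 and 8.6 are scheduled from the start of radiotherapy, and the footnote to section 10.3 times the toxicity endpoints from treatment start.

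Section 10.5 has the data monitoring committee review accumulating safety data at least once a year. It gives no rule for putting SAEs from the three groups on a common time base.

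**The concern.** A window tied to the last fraction lasts longer, from the start of treatment, in the group that is treated longer. A non-fatal hospital admission on day 42 is an SAE in a control patient and is not one in a test patient. If the committee sees SAE counts or proportions by arm, control has had two more weeks in which to collect events. That tilts the comparison towards the experimental schedules, which is the less cautious direction for a safety review.

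The tilt arises at collection, so an analysis plan could not fully undo it. The 7-week duty in section 9.2 covers only the sub-study, about 345 of 4830 participants. For the other 93% or so, section 8.6 schedules no clinician toxicity assessment between radiotherapy and the lung assessment at 3 months.

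**Working it through.** **Inputs.** Control has 15 fractions over 3 weeks and the test groups 5 fractions over 1 week (sections 3 and 8.5). The tail is 30 days after the last fraction (9.1, 9.3). On start day, section 8.14 says: "Treatment can start on any day of the week". I assume that fractions are given on weekdays only.

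**The protocol's own offset.** In the timing table of section 8.6, the week 7 assessment falls "28 days after final fraction" in control and 42 days after it in the test groups. With the last fraction at the end of week 3 or week 1, this is (7 − 3) × 7 = 28 and (7 − 1) × 7 = 42. The offset is 42 − 28 = 14 days, and it carries straight over to the SAE window.

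**Window length, counting the start day as day 1.** Length = day of last fraction + 30.

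| Start | Control | Test | Difference | Ratio |
|---|---|---|---|---|
| Monday | 19 + 30 = 49 | 5 + 30 = 35 | 14 | 1.40 |
| Tuesday to Friday | 21 + 30 = 51 | 7 + 30 = 37 | 14 | 1.38 |

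**What a constant daily hazard would imply (illustration only).** The protocol states no SAE rate, so the control risks below are assumptions. With the same hazard in every arm and a Monday start, test risk = 1 − (1 − p)^(35/49), where p is the 49-day control risk. Patients with an SAE are given per 1610.

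| Assumed control risk | Apparent test risk | Control patients | Test patients |
|---|---|---|---|
| 1% | 0.72% | 16.1 | 11.5 |
| 2% | 1.43% | 32.2 | 23.1 |
| 3% | 2.15% | 48.3 | 34.6 |
| 5% | 3.60% | 80.5 | 57.9 |

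**Why the hazard is unlikely to be constant.** Section 1.1 puts the peak of acute side-effects 2 to 4 weeks after radiotherapy. For a Monday start this is days 19 + 14 = 33 to 19 + 28 = 47 in control, and days 5 + 14 = 19 to 5 + 28 = 33 in the test groups. The 30-day tail covers both peaks. The 14 extra days in control are therefore extra time on treatment, and the surplus of events would be mainly intercurrent or related to systemic therapy.

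**Whether analysis alone can repair it.** Cutting both arms at day 35 equalises the length, but it keeps the whole test peak and only days 33 to 35 of the control peak. A rate per person-day is a fair comparison only if the hazard is roughly constant, which the stated peak argues against. A cut at day 49 covers both peaks, but test-group SAE data end at day 35 to 37.

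**The case against.** The strongest reply is that nothing planned is affected. SAEs are not an endpoint in sections 4 or 10.3, and section 10.4 specifies no between-arm SAE comparison. The toxicity comparisons there run from treatment start. Both toxicity stopping guidelines in section 10.5 use CTCAE or RTOG gradings against fixed rates. Section 9.3 is a reporting duty, and how SAE tables are cut is normally left to the analysis plan or the committee's report. All of that stands, and it is why this is an improvement and not a threat to the trial's conclusions.

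A second reply is that tying the window to the last fraction is a reasonable choice, because it gives every arm the same 30 days after radiotherapy and covers the stated acute peak. That also stands. A common 7-week window equalises time from start at the price of a longer post-radiotherapy tail in the test groups: 49 − 5 = 44 days against 30 in control for a Monday start. The wording proposed below keeps the 30-day tail in every arm and accepts this trade-off.

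A third reply is that late events in test patients are not all lost. Deaths are captured through overall survival, and sub-study patients still report adverse events to week 7. This narrows the gap to non-fatal serious events at about days 36 to 49 in test patients outside the sub-study, but does not close it.

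**Conclusion.** The SAE window from treatment start is 14 days shorter in the test groups, 35 to 37 days against 49 to 51. This follows from the protocol's own schedule and the weekday assumption. Raw by-arm SAE counts or proportions would tend to favour the 1-week schedules. How strongly cannot be said: the figures above rest on assumed SAE risks and a constant daily hazard, and the effect on radiotherapy-related events should be smaller than they suggest.

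Three stronger readings are tempting and are not supported.

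- A reader might infer that every between-arm SAE comparison is biased, or that a 40% higher SAE rate in a test group would go unseen. A comparison over equal time does not have the length bias, and the 1.4 ratio needs a constant hazard and a crude proportion.
- A reader might infer that all other acute measures are timed from treatment start. They are not: the later blood samples of the translational sub-study follow the end of radiotherapy (section 18.1), and pregnancy reporting runs to 30 days after treatment (section 9.8).
- A reader might infer that pneumonitis is missed, because section 1.1 describes it as "peaking around 3 months after radiotherapy in up to 2% of patients needing radiotherapy to lymph nodes behind the breastbone", beyond the SAE window. That limit is the same in all arms, so it causes no imbalance. Pneumonitis is covered by the 3-month RTOG assessment for all participants, the powered internal mammary chain analysis (section 10.1) and its stopping guideline. Longer SAE reporting for lung events is not called for on this ground.

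**What to change.** In sections 9.1 and 9.3, define and report SAEs in every group until the later of 7 weeks from the first fraction, the clock already used in section 9.2, or 30 days after the last fraction. State that by-arm SAE summaries, including those for the data monitoring committee, use the common first 7 weeks from treatment start.

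Control is unchanged, since its window already reaches day 49 to 51. Each test-group patient gains 49 − 35 = 14 days of SAE reporting for a Monday start, or 49 − 37 = 12 days otherwise. The cost is a wording amendment, some extra SAE forms from the test groups, and a longer post-radiotherapy tail there than in control. No visits are added. The change works only prospectively, because events that were never reported as SAEs cannot be recovered reliably later.
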